4.3 JUSTIFICATION FOR DOSE

Dose escalation for SAR444245 monotherapy and in combination with pembrolizumab or cetuximab is ongoing in the first-in-human HAMMER study. Data from a total of 68 patients who have received SAR444245 Q2W or Q3W in monotherapy, in a Q3W regimen in combination with pembrolizumab 200 mg Q3W, or with cetuximab 400/250 mg/m² QW is available as of 18 June 2021. HAMMER Safety Review Committee have cleared SAR444245 24 µg/kg Q3W pembrolizumab combination dose level based on this data cut-off.

The dose levels tested to date for SAR444245 monotherapy administered using a Q3W schedule are 8 µg/kg (n=4), 16 µg/kg (n=6), 24 µg/kg (n=11), 32 µg/kg (n=6) and 40 µg/kg (n=2).

In combination with pembrolizumab, SAR444245 has been administered Q3W at the doses of 8 µg/kg (n=4), 16 µg/kg (n=9), 24 µg/kg (n=6), 32 µg/kg (n=1). In combination with cetuximab, SAR444245 has been administered Q3W at 16 µg/kg (n=5) or 24 µg/kg (n=5).

For monotherapy cohort, the only DLT observed to date is a Grade 3 infusion reaction (occurred on C2D1 which resolved on the same day with supportive care) reported in a patient on 32 µg/kg Q3W monotherapy.

For SAR444245 in combination with pembrolizumab 200 mg Q3W, 1 DLT (Grade 3 liver enzyme elevation with Grade 2 bilirubin elevation meeting drug-induced liver injury [DILI] criteria occurred on C1D1 which resolved after 7 days with steroids) was observed in a participant with SAR444245 24 µg/kg Q3W with pembrolizumab.

No DLTs were reported by SAR444245 cetuximab combination cohort (SAR444245 24 µg/kg Q3W).

Grade 3/4 TEAEs commonly reported by participants who received SAR444245 24 µg/kg monotherapy (n=11) include in particular Grade 4 lymphocyte count decreased/lymphopenia (7 participants, 63.6%) and Grade 3 anemia (3 participants, 27.3%) and Grade 3 dyspnea (2 participants, 18.2%). Of note, transient lymphocyte count decrease in the peripheral blood is an expected effect, consequence of T cell activation and temporary compartmental redistribution after IL-2 treatment. Nevertheless, this phenomenon is reported as an adverse event (AE) in HAMMER study.

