8.3.8 Adverse event of special interest

Adverse event of special interest

An AESI is an AE (serious or nonserious) of scientific and medical concern specific to the Sponsor's product or program, for which ongoing monitoring and immediate notification by the Investigator to the Sponsor is required. Such events may require further investigation in order to characterize and understand them. Adverse events of special interest may be added, modified or removed during a study by protocol amendment. The following events need to be reported as AESIs:

- Pregnancy of a female participant entered in a study as well as pregnancy occurring in a female partner of a male participant entered in a study with IMP/NIMP
 - Pregnancy occurring in a female participant entered in the clinical trial or in a female partner of a male participant entered in the clinical trial. It will be qualified as an SAE only if it fulfills one of the seriousness criteria (see Appendix 3 [[Section 10.3](#)]).
 - In the event of pregnancy in a female participant, IMP should be discontinued.
 - Follow-up of the pregnancy in a female participant or in a female partner of a male participant is mandatory until the outcome has been determined (See Appendix 4 [[Section 10.4](#)]).
- Symptomatic overdose (serious or nonserious) with IMP/NIMP
 - An overdose of IMP is defined as: increase of at least 30% of the dose to be administered in the specified duration or if the dose is administered in less than half the recommended duration of administration.
 - An overdose (accidental or intentional) with the NIMP is an event suspected by the Investigator or spontaneously notified by the participant (not based on systematic pills count) and defined as at least twice the intended dose within the intended therapeutic interval, adjusted according to the tested drug.
- An elevated AST or ALT lab value that is greater than or equal to 3X the ULN and an elevated total bilirubin lab value that is greater than or equal to 2X the ULN and, at the same time, an alkaline phosphatase lab value that is less than 2X the ULN, as determined by way of protocol-specified laboratory testing or unscheduled laboratory testing*.

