*Note: These criteria are based upon available regulatory guidance documents. The purpose of the criteria is to specify a threshold of abnormal hepatic tests that may require an additional evaluation for an underlying etiology. The trial site guidance for assessment and follow up of these criteria can be made available. It may also be appropriate to conduct additional evaluation for an underlying etiology in the setting of abnormalities of liver blood tests including AST, ALT, bilirubin, and alkaline phosphatase that do not meet the criteria noted

above. In these cases, the decision to proceed with additional evaluation will be made through consultation between the study investigators and the Sponsor.

- Other project-specific AESIs
 - IRR Grade ≥ 2
 - CRS Grade ≥ 2
 - ICANS of any grade
 - VLS of any grade
 - Any immune-related AE Grade ≥ 3
 - Arrhythmia Grade ≥ 3

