c Death within 30 days from last IMP administration and for whom cause of death is not disease progression or the death occurred more than 30 days from last IMP administration and the cause of death is AE

Analysis of deaths

In addition to the analyses of deaths included in [Table 8](#) the number (%) of participants in the following categories will be provided:

- Deaths during the treatment-emergent and post-treatment periods by main reason for death
- An overview of Grade 5 AEs will be provided with the following categories:
 - Grade 5 AE (TEAE and post-treatment).
 - Fatal TEAE (regardless of date of death/period).
 - Grade 5 TEAE with a fatal outcome during the treatment-emergent period,
 - Any Grade TEAE with a fatal outcome during the post-treatment period.

- Post-treatment Grade 5 AE (excluding a TEAE that worsened to Grade 5 during the post-treatment period).

Analysis of adverse events of special interest (AESIs)

Number (%) of participants experiencing at least one adverse event of special interest will be provided, by SOC and PT. The selection will be made using the eCRF specific **AESI** tick box. Tables will be sorted as indicated in [Table 7](#).

In addition, the following analyses will be done for infusion reactions categories (i.e., infusion related reactions (IRRs), cytokine release syndrome (CRS) , flu-like symptoms (FLS) and anaphylaxis):

- Description of the infusion reactions by predefined grouping and other reported PT.
- Worst grade
- Action taken for each IMP
- Corrective treatment given (Yes, No)
- Number (%) of patients with only 1 episode, ≥ 2 , ≥ 3 , ≥ 4 and ≥ 5 episodes
- Onset of first episodes of infusion reaction (at the first infusion and subsequent infusions)
- Number (%) of patients with infusion reactions (any episodes) at the first and subsequent infusions
- Number (%) of patients with at least one infusion with two episodes of infusion reaction
- Total number of infusion reaction episodes
- Time to onset from infusion (by category: Infusion Day/1 day after infusion/ 2 to 3 days from infusion/ More than 3 days from infusion when applicable)
- Duration of infusion reaction (in days) (by category 1 day/ 2 to 3 days/ More than 3 days/not recovered)
- Number (%) of patients with infusion reactions' symptoms (as reported by investigator) by SOC and PT.

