3.6.3 Additional safety assessments

3.6.3.1 Laboratory variables, vital signs

The following laboratory variables and vital signs variables will be analyzed. They will be converted into standard international units.

- Hematology:
 - Red blood cells and platelets: hemoglobin, hematocrit, platelet count
 - White blood cells: leukocytes, neutrophils, lymphocytes, monocytes, basophils, eosinophils

- Clinical chemistry:
 - Metabolism: glucose, albumin, lipase, amylase
 - Electrolytes: sodium, potassium, chloride, calcium corrected, bicarbonate, magnesium
 - Calcium Corrected (mmol/L) = Total calcium (mmol/L) + 0.8 * 0.25 * [4 – Serum albumin (g/L) * 0.1]
 - Renal function: creatinine, eGFR, blood urea nitrogen
 - Liver function: alanine aminotransferase, aspartate aminotransferase, alkaline phosphatase, lactate dehydrogenase, bilirubin
- Vital signs: heart rate, systolic and diastolic blood pressure, respiratory rate, temperature, ECOG Performance status

Data below the lower limit of quantitation/detection limit (LLOQ) will be replaced by half of the LLOQ, data above the upper limit of quantification will be replaced by ULOQ value.

For hematological parameters and some selected biochemistry parameters, Sanofi sponsor generic ranges (LLN, ULN) are defined and will be used for grading (see list of parameters in [Section 5.4](#)). For other biochemistry parameters, grading will be derived using local laboratory normal ranges.

Quantitative analyses

When relevant, for laboratory variables and vital signs above, descriptive statistics for results and changes from baseline will be provided for the last value and the worst value (minimum and/or maximum value depending on the parameter) during the on-treatment period. These analyses will be performed using local measurements for laboratory variables.

Analyses according to PCSA and NCI grading

For laboratory variables, analyses according to NCI grading will be made based on NCI-CTCAE version 5.0. In addition, for eGFR, blood urea nitrogen, hematocrit, monocytes, basophils and chloride, PCSA analyses will be performed based on the PCSA list currently in effect at Sanofi at the time of the database lock.

Analyses according to PCSA and NCI grading will be performed based on the worst value during the treatment-emergent period, using all measurements (either local or central, either scheduled, nonscheduled or repeated).

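### AESIs are selected by the eCRF tick box alone, so a concurrent liver-test AESI that a site does not tick cannot be identified in any output the SAP plans

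*SAP*

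**What the plan says.** SAP 3.6.2 plans a count of participants with at least one AESI, by SOC and PT. "The selection will be made using the eCRF specific" AESI tick box. It states no derivation from grades or laboratory values and no reconciliation against them.

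Master protocol 8.3.8 lists nine AESIs:

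- pregnancy;
- symptomatic overdose;
- the liver criterion, which begins "An elevated AST or ALT lab value that is greater than or equal to 3X the ULN and an elevated total bilirubin lab value" and goes on to set bilirubin at 2x ULN or more with ALP below 2x ULN at the same time, "as determined by way of protocol-specified laboratory testing or unscheduled laboratory testing";
- six under "Other project-specific AESIs": IRR Grade 2 or higher, CRS Grade 2 or higher, "ICANS of any grade", VLS of any grade, immune-related AE Grade 3 or higher, and arrhythmia Grade 3 or higher.

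On laboratory data, SAP 3.6.3.1 lists the liver tests as separate parameters: "Liver function: alanine aminotransferase, aspartate aminotransferase, alkaline phosphatase, lactate dehydrogenase, bilirubin". Each is graded by NCI-CTCAE on its worst treatment-emergent value. The laboratory parameters named for PCSA analysis include no liver test: "In addition, for eGFR, blood urea nitrogen, hematocrit, monocytes, basophils and chloride, PCSA analyses will be performed".

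**The concern.** The selection rule counts what sites flagged, while the protocol defines several AESIs by criteria that the database can test. For most of them an unticked event would still surface elsewhere under its own preferred term. The liver AESI is different. It exists only as a combination of three or four test results at one time, and nothing else in the SAP forms that combination.

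There are plausible routes to a missed tick. Master protocol 8.2.4 treats abnormal laboratory findings linked to the underlying disease as not clinically significant unless the investigator judges them worse than expected. Exclusion criterion E 30 admits participants with liver lymphoma at ALT/AST up to 5x ULN, already above the AESI cut of 3x.

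The safety profile is a secondary objective. Protocol 4.3 also reports one combined liver event at 24 µg/kg with pembrolizumab, Cohort A's starting regimen, "meeting drug-induced liver injury [DILI] criteria occurred on C1D1 which resolved after 7 days with steroids". A concurrent liver signal is therefore something Cohort A should be able to count reliably.

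**Working it through.** **1. How many AESIs have checkable criteria.** Of the nine, five carry an explicit threshold: liver, IRR, CRS, immune-related AE and arrhythmia. ICANS and VLS count at any grade, which makes seven of nine defined by grade, term or laboratory value. An immune-related AE also needs a judgement about cause, so term and grade alone do not settle it.

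**2. Can the separate laboratory tables recover the liver AESI?** With a participants above a cut on one test and b on another, out of n, the number above both lies between max(0, a + b − n) and min(a, b). As an illustration, take a = 4 with raised ALT, b = 3 with raised bilirubin and n = 25. The bounds are max(0, −18) = 0 and min(4, 3) = 3, or 0% to 12%. The tables do not say where in that range the truth lies.

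Even the overlap would not be the AESI:

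- The footnotes to Substudy 01 Table 6 put Grade 2 bilirubin at >1.5 to 3.0x ULN (normal baseline), which straddles the AESI cut of 2x.
- With an abnormal baseline, the same footnotes grade ALT/AST against baseline. A participant entering at 2x ULN (allowed by E 30) who rises to 4x ULN is at 4/2 = 2x baseline. That is below the Grade 2 band of >3x baseline, yet above the AESI cut of 3x ULN.
- Worst values of two tests need not fall at the same time.
- The condition on ALP is not applied.

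**3. Other outputs.** The DLT criterion in protocol 4.1 pairs transaminases with bilirubin >2x ULN, but it needs Grade 3 or higher ALT/AST and covers only the run-in observation period. TEAE tables would show component terms if they were reported as AEs, but not that they coincided.

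**4. Size per case.** 1/25 = 4 percentage points.

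**5. Effect on detection.** The SAP's own figures reproduce: 1 − (1 − p)^25 is 22.2%, 39.7% and 72.3% for p = 1%, 2% and 5%. If a proportion s of qualifying cases is ticked, p becomes p × s. No value of s is in the documents, so the range below is an assumption.

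| s | P(at least 1 shown in 25), true incidence 5% |
|---|---|
| 100% | 72.3% |
| 90% | 68.4% |
| 80% | 64.0% |
| 50% | 46.9% |

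**6. Direction.** Ticks on non-qualifying events work the other way. With true incidence π and a false-tick rate f among the rest, the shown incidence is π·s + (1 − π)·f. For π = 10% and s = 80%:

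- f = 0 gives 8.0%;
- f = 2% gives 8.0 + 1.8 = 9.8%;
- f = 5% gives 8.0 + 4.5 = 12.5%.

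The sign of the net error therefore depends on both kinds of ticking error.

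**The case against.** The protocol places real duties on sites. AESIs go to the sponsor within 24 hours (8.3.1). Specific events meeting the definition must be documented in the eCRF (substudy 6.5.4). Investigators review each laboratory report (8.2.4), and source data are verified (10.1.8). By definition an AESI is an event the investigator notifies, so a site flag is a legitimate starting point. Reconciliation may also be described in monitoring documents outside the two reviewed here. All of this stands, and it limits how many missed ticks to expect. It does not give the SAP an output in which a missed liver case would show.

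Most other AESIs are visible anyway. IRR and CRS have their own description by grouping and worst grade in SAP 3.6.2. ICANS, VLS and arrhythmia would appear by PT in the TEAE tables. That also stands, and it is why the liver AESI is the main gap.

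SAP 3.6.3.1 later speaks of PCSA incidence for the laboratory variables above, using a list held outside the SAP. If that list were meant to cover a combined liver criterion, the SAP would need to say so. The parameters it names do not include a liver test.

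Three stronger readings are tempting and not supported:

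- *AESI incidence is understated.* No document shows a missed tick, and false ticks would raise the count.
- *Every AESI can be derived.* Immune-related attribution requires excluding other causes (Substudy 01, 6.5.4.4), and pregnancy and symptomatic overdose are not defined by grade.
- *The one liver DLT among 6 participants can be scaled to Cohort A.* It is a single case, with an exact 95% CI of about 0.4% to 64%. Its Grade 2 bilirubin may lie below 2x ULN, and ALP is not given. It was also identified and reported, so it is not evidence of under-reporting.

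**Conclusion.** The point holds in a limited form. Tick-box selection leaves the liver AESI without any check in the SAP, because its definition is concurrent and numerical while the laboratory analysis takes one parameter at a time. AESI incidence can be misstated, most plausibly downward for the liver AESI, by 4 percentage points per missed case in a cohort of 25. The actual size is unknown because the tick rate is not given, and the detection figures rest on assumed rates. The effect is confined to a descriptive safety table. No sample size, efficacy estimate or run-in dose rule depends on it. It is worth correcting because the correction is cheap and uses data the trial already collects.

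**What to change.** In SAP 3.6.2:

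1. Derive the liver AESI by program from post-baseline ALT/AST, total bilirubin and ALP, using scheduled and unscheduled values. SAP 3.6.3.1 already uses all such measurements and local normal ranges for grading. Define what counts as the same time; same sampling date is the simplest choice.
2. Count a participant for the liver AESI if ticked or derived.
3. Check the AESIs that can be derived from term and grade against the tick box: CRS and IRR Grade 2 or higher, ICANS and VLS of any grade, and arrhythmia Grade 3 or higher.
4. List discordant cases in both directions: criteria met but not ticked, and ticked but criteria not met. Counting ticked or derived can only raise the number, so the second list matters. Show baseline liver values, since E 29 and E 30 allow some participants to enter with raised tests.
5. Leave immune-related attribution, pregnancy and symptomatic overdose to the tick box.

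The cost is a paragraph of SAP text and modest programming, with no new data collection. AESI counts may change slightly, and discordant cases will need medical review.

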3.6.3 Additional safety assessments

3.6.3.1 Laboratory variables, vital signs

The following laboratory variables and vital signs variables will be analyzed. They will be converted into standard international units.

- Hematology:
 - Red blood cells and platelets: hemoglobin, hematocrit, platelet count
 - White blood cells: leukocytes, neutrophils, lymphocytes, monocytes, basophils, eosinophils

- Clinical chemistry:
 - Metabolism: glucose, albumin, lipase, amylase
 - Electrolytes: sodium, potassium, chloride, calcium corrected, bicarbonate, magnesium
 - Calcium Corrected (mmol/L) = Total calcium (mmol/L) + 0.8 * 0.25 * [4 – Serum albumin (g/L) * 0.1]
 - Renal function: creatinine, eGFR, blood urea nitrogen
 - Liver function: alanine aminotransferase, aspartate aminotransferase, alkaline phosphatase, lactate dehydrogenase, bilirubin
- Vital signs: heart rate, systolic and diastolic blood pressure, respiratory rate, temperature, ECOG Performance status

Data below the lower limit of quantitation/detection limit (LLOQ) will be replaced by half of the LLOQ, data above the upper limit of quantification will be replaced by ULOQ value.

For hematological parameters and some selected biochemistry parameters, Sanofi sponsor generic ranges (LLN, ULN) are defined and will be used for grading (see list of parameters in [Section 5.4](#)). For other biochemistry parameters, grading will be derived using local laboratory normal ranges.

Quantitative analyses

When relevant, for laboratory variables and vital signs above, descriptive statistics for results and changes from baseline will be provided for the last value and the worst value (minimum and/or maximum value depending on the parameter) during the on-treatment period. These analyses will be performed using local measurements for laboratory variables.

Analyses according to PCSA and NCI grading

For laboratory variables, analyses according to NCI grading will be made based on NCI-CTCAE version 5.0. In addition, for eGFR, blood urea nitrogen, hematocrit, monocytes, basophils and chloride, PCSA analyses will be performed based on the PCSA list currently in effect at Sanofi at the time of the database lock.

Analyses according to PCSA and NCI grading will be performed based on the worst value during the treatment-emergent period, using all measurements (either local or central, either scheduled, nonscheduled or repeated).

For laboratory variables and vital signs above, the incidence of participants with at least one PCSA during the treatment-emergent period will be summarized regardless of the baseline level and according to the following baseline status categories:

- Normal/missing
- Abnormal according to PCSA criterion or criteria

For laboratory variables graded by NCI-CTCAE,

- The number (%) of participants with abnormal laboratory tests at baseline will be presented by grade.
- The number (%) of participants with abnormal laboratory tests during the treatment-emergent period will be summarized by grade. When appropriate, the number (%) of participants with abnormality of any grade and with Grade 3-4 abnormalities will be provided.

3.7 OTHER ANALYSES

3.7.1 Other variables and/or parameters

3.7.1.1 PK analyses

No PK parameters will be assessed, as only sparse sampling for pharmacodynamic concentrations of SAR444245 is implemented in the study.

Table 9 - List of PK concentrations and definitions

PK concentrations	SAR444245	Definition
C_{eo1}	X	concentration sample taken at EOI
C_{D2}	X	concentration sample taken any time at day 2 after previous administration
C_{D3}	X	concentration sample taken any time at day 3 after previous administration

Applicable concentrations will be described on the PK population for each planned visit using the following descriptive statistics: mean, geometric mean, median, standard deviation, coefficient of variation, minimum, and maximum. These analyses will be performed by specific subgroups (e.g., gender, BMI, age) if appropriate.

All concentration values below the lower limit of quantitation (LLOQ) will be treated as zero in all summary statistics. Geometric mean will not be computed in case at least one concentration is below LLOQ.

3.7.1.2 Immunogenicity analyses

Participant's ADA status, response variable and kinetics of ADA responses (see definitions below) will be summarized on the ADA population.

Kinetics of ADA responses will be described for participants with treatment-induced ADA and for participants with treatment-boosted ADA, separately. Time to ADA onset and duration of ADA will be described with minimum, Q1, median, Q3 and maximum statistics.

Peak titer will be described with minimum, Q1, median, Q3 and maximum statistics for participants with treatment-induced ADA and for participants with treatment-boosted ADA, separately.

ADAs against SAR444245 (negative, positive, inconclusive) and corresponding titers, ADAs directed against PEG moiety of SAR444245 status (negative, positive,) and ADAs cross-reacting with endogenous IL-2 status (negative, positive) will also be described overtime using descriptive statistics.

ADAs directed against PEG moiety of SAR444245 status and ADAs cross-reacting with endogenous IL-2 status will only be determined if ADAs against SAR444245 status is positive.

The impact of positive immune response on efficacy, PK and safety variables may be further explored, depending on ADA incidence.

Participant's ADA status against SAR444245

- Participants with **pre-existing ADAs** correspond to participants with ADAs present in samples drawn before first administration of intervention. Participants with missing ADA sample at baseline will be considered as without pre-existing ADA.
- Participants with **treatment-emergent ADA** correspond to participants with at least one treatment-induced/boosted ADA.
 - Participants with **treatment-induced ADAs** correspond to participants with ADAs that developed during the treatment-emergent (TE) period and without pre-existing ADA (including participants without pre-treatment samples).
 - Participants with **treatment-boosted ADAs** correspond to participants with pre-existing ADAs that are boosted during the TE period to a significant higher titer than the baseline. A 2-fold serial dilution schema is used during titration, so at least a 4-fold increase will be considered as significant.
- Participants with **unclassified ADA** correspond to participants with pre-existing ADAs that cannot be classified as treatment-boosted ADA because of missing titer(s) (i.e., a positive ADA sample during the TE period in a participant with pre-existing ADA but with missing titer at this sample or at baseline).
- Participants **without treatment-emergent ADA** correspond to participants without treatment-induced/boosted ADA and without any inconclusive sample nor unclassified ADA during the TE period.
- Participants **with inconclusive ADA** are defined as participants which cannot irrefutably be classified as with or without treatment-emergent ADA.

Kinetics of ADA response

[figure not shown]
Kinetics of ADA response will be derived for participants with treatment-induced/boosted ADA considering ADA samples collected during the TE period and post-treatment period.

- **Time to onset of ADA response** is defined as the time period between the first IMP administration and the first treatment-induced/boosted ADA.
- **Duration of ADA response** is defined as the time between the first treatment-induced/boosted ADA and the last treatment-induced/boosted ADA, irrespective of negative samples or positive samples not reaching the boosted threshold in-between. ADA duration will be summarized only for participants with persistent ADA response.
 - A positive sample (boosted positive sample for participants with pre-existing ADA) occurring after the TE period will be considered as treatment-induced/boosted ADA if a previous treatment-induced/boosted ADA occurred during the TE period and less than 16 weeks before this sample.
- **Persistent ADA response** is defined by treatment-induced/boosted ADA with a duration of ADA response of at least 16 weeks.
- **Transient ADA response** is defined by treatment-induced/boosted ADA with a duration of ADA response of less than 16 weeks and the last sample of the TE period is not treatment-induced/boosted.
- **Indeterminate ADA response** is defined by treatment-induced/boosted ADA that are neither persistent nor transient.

ADA response variable:

- **ADA incidence** is defined as the proportion of participants found to have seroconverted (treatment-induced ADAs) or boosted their pre-existing ADA response (treatment-boosted ADAs) at any time point during the TE period.
- **Incidence of ADAs** directed against PEG moiety of SAR444245 is defined as the proportion of participants with ADAs directed against PEG moiety of SAR444245 during the TE period among evaluable participants. Participants from ADA population are evaluable for ADAs directed against PEG moiety except if ADAs directed against PEG moiety status is not determined on an ADA against SAR444245 positive sample
- **Incidence of ADAs cross-reacting with endogenous IL-2** is defined as the proportion of participants with ADAs directed against endogenous IL-2 during the TE period among evaluable participants. Participants from ADA population are evaluable for ADAs directed against endogenous IL-2 except if their status is not determined on an ADA against SAR444245 positive sample.

